3.3.3.2 Definition of re-excisions

A re-excision is defined as a surgical procedure performed in the ipsilateral breast following the primary lumpectomy because of positive margins found from the initial lumpectomy procedure. The re-excision procedure can be a separate surgical procedure to excise further breast tissue or a mastectomy.

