15.1 Analysis Populations

- Safety (SAF) Population: the safety population includes all subjects who received study drug (LUM015).
- Modified Intent To Treat (mITT) population: includes the subjects in SAF, but excluding subjects who are not able to be imaged with the LUM Imaging System. The mITT population will be used as the primary analysis population for the three co-primary efficacy endpoints and efficacy analysis of the secondary endpoints.
- Per-Protocol Population: Includes mITT subjects who complete all study evaluations and are without any major protocol deviations that may impact data collection or efficacy analysis. A sensitivity analysis of the primary and secondary efficacy endpoints will be conducted using the per-protocol analysis set.

15.2 Definition of truth standard for diagnostic performance evaluation (sensitivity and specificity)

We propose to use a hierarchical approach to determine the truth standard as therapeutic shaves were taken only when the LUM imaging system signaled positive for potential residual tumor. The highest truth standard is whether pathology finds cancer in a tissue shave removed from the area that was imaged in the cavity. When a shave does not exist, then whether tumor is found in a re-excision surgery is considered as the truth standard. When neither a shave nor a second surgery exists for a given orientation that was imaged, the margin assessment of that orientation is used as truth standard. **Error! Reference source not found.** shows a schematic for determination of the truth standard.

LUMICELL CONFIDENTIAL

This document is confidential. Do not disclose or use except as authorized.

[figure not shown]

Figure 6: Definition of truth standard to evaluate the LUM Imaging System diagnostic performance.

When the therapeutic shave is not available and the follow-up surgery is performed, only the pathology from the first-time re-excision at the tissue/orientation level will be used for hierarchical sensitivity/specificity evaluation.

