3.1 Definition of positive margins

For this study, positive margins are defined using the latest consensus from the Society of Surgical Oncology as follows:

- For invasive cancer with or without associated ductal carcinoma in situ (DCIS): cancer cells or DCIS present on ink [1]
- For pure DCIS lesions: DCIS present less than 2 mm from the ink [2]. Note: when microinvasive cancer is reported, the positive margin criterion will be the same as for pure DCIS instead of the criterion for invasive cancer per NCCN Clinical Practice Guidelines in Oncology.

LUMICELL CONFIDENTIAL

This document is confidential. Do not disclose or use except as authorized.

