3.2.2 Sensitivity and specificity

The instrument diagnostic accuracy is measured by sensitivity and specificity on a per-tissue basis. Because a LUM-guided shave does not exist when a negative LUM image is indicated we propose a hierarchical approach to determine the truth standard as depicted in Figure 2. The highest truth standard is whether pathology finds cancer in a tissue shave removed from the area that was imaged in the cavity. When a shave does not exist, then whether tumor is found in a re-excision surgery is considered as the truth standard. When neither a shave nor a second surgery exists for a given orientation that was imaged, the margin assessment of that orientation is used as truth standard. We believe that the hierarchical approach outlined to determine the truth standard is the most meaningful and practical assessment of device accuracy to predict the presence of cancer in the cavity.

LUMICELL CONFIDENTIAL

This document is confidential. Do not disclose or use except as authorized.

True positive = truth standard positive & Lum cavity image positive
 False negative = truth standard positive & Lum cavity image negative
 True negative = truth standard negative & Lum cavity image negative
 False positive = truth standard negative & Lum cavity image positive

Figure 2: Definition of truth standard to evaluate the LUM Imaging System diagnostic performance.

When a therapeutic shave and re-excision are not available for a given orientation, the margin from the prior resected tissue of the corresponding orientation will be used as ground inferred truth for evaluation (Figure 3). The number of prior positive margins contributing to the ground inferred truth for a patient will not exceed the number of orientations with positive margins.

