The orientation of the tissue removed during a re-excision is typically noted in the pathology report and matches the orientation in which a positive margin was identified from the initial surgery. However, based on our prior experience there will be instances in which the orientation of the tissue removed during a re-excision is not specified. In cases of unclear orientation of the tissue removed during re-excisions, it will be assumed that the re-excision was intended to address only the orientations with positive margins and pathology findings from the re-excisions (tumor found/not found) will be applied to those orientations. Also, if there are two consecutive shaves during the re-excision from overlapping orientations, they will be considered as one.

If a mastectomy is performed as a follow-up surgery and no cancer is found in the mastectomy specimen, all the orientation will be considered as cancer negative for truth standard. If a mastectomy is performed and cancer is found but there is no indication on the orientation in which the cancer was found, the orientation in which a positive margin was identified in the initial lumpectomy will be considered as cancer positive for truth standard unless otherwise noted.

The diagnostic performance will be computed by using the hierarchical approach to populate the 2x2 contingency table (Table 1). The Youden Index will be reported but is not hypothesis-tested.

LUMICELL CONFIDENTIAL

This document is confidential. Do not disclose or use except as authorized.

Table 1: Definitions for 2x2 contingency table.

	Hierarchical Truth standard (+)	Hierarchical Truth standard (-)
LUM positive cavity signal (+)	True Positives	False Positives
LUM negative cavity signal (-)	False Negatives	True Negatives

$$\text{sensitivity} = \frac{\text{True Positives}}{\text{True Positives} + \text{False Negatives}}$$

$$\text{specificity} = \frac{\text{True Negatives}}{\text{True Negatives} + \text{False Positives}}$$

$$\text{Youden Index} = \text{sensitivity} + \text{specificity} - 1$$

[figure not shown]

Figure 3: Depiction of the prior margin assessment for the LUM signal in the cavity when no additional tissue from the cavity is available.

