4.11.3 Missing and spurious data

During LUM-guided imaging, when there is not enough tissue to be removed (e.g. too close to skin or too close to the chest wall) no LUM image shall be recorded because it does not generate an actionable result.

In the case where the LUM Imaging System indicates that a therapeutic shave needs to be removed but the surgeon decides not to follow this guidance, the reason for not doing so will be recorded in the patient's CRF or during imaging. These instances are considered as a protocol deviation. There are other cases when the LUM-guide shave reach the protocol limit of 2 guided shaves per orientation, so a third guided shave will not be performed. In these cases, the data will be included in the performance evaluation as is; that is, because these will not generate a LUM-guided shave they will not be evaluated as removing cancer or converting positive margins to negative margins. However, they will be evaluated for the per-tissue sensitivity and specificity calculation according the hierarchical approach described in section 3.2.2.

In occasions, a cavity image may be recorded from an unintended region or the image may be deemed as low quality (blurry, out of focus, etc.). For example, the surgeon realizes that he/she placed the device in the wrong location within the cavity after recording an image. Since the LUM software does not allow to overwrite saved images, the error images will be labeled as "image error delete", and the image will be excluded from the analysis.

Other specific cases will be handled as described below.

- a. When a patient was prescribed Letrozole adjuvant therapy prior to surgery, the patient will be removed from the device performance evaluation (major protocol deviation) in the per-protocol analysis but will be included in the mITT population for primary analysis.
- b. When the time from injection of LUM015 to initial imaging time is greater than 6 hours due to unplanned surgical delays, the patients will be removed from the device performance evaluation (major protocol deviation) in the per-protocol analysis but will be included in the mITT population for primary analysis.
- c. For the re-excision rate endpoints, all patients undergoing a re-excision will be included in the analysis.
- d. In the case of a therapeutic shave taken but no image saved before the shave was removed, the shave will be excluded from analysis but will be included in the estimation of final margin.

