- e. In the case of a SOC shave taken but no image saved before the shave was removed, the shave will be excluded from analysis but will be included in the estimation of SOC margin.
- f. In the case of a protocol deviation where an SOC shave is taken after use of the LUM Imaging System, the analysis will be as follows:

LUMICELL CONFIDENTIAL

This document is confidential. Do not disclose or use except as authorized.

- i. For per tissue sensitivity and specificity: if there is a Lumicell image for this SOC shave, then the SOC shave will be used as truth standard for that orientation. If there is no Lumicell image, then the SOC shave will not be used for sensitivity and specificity evaluation.
- ii. For margin assessment analysis: for the calculation of the SOC margin status versus the margin status after Lumicell, the margin of that SOC shave will be excluded.
- g. In the case of a patient having bilateral lumpectomy, only the data collected from the side of the breast that was imaged will be included in the device performance evaluation.
- h. In the case of an unknown dimension of a shave, the volume of the shave will be assigned as the average volume of that of all the existing shaves of the corresponding type (SOC or therapeutic shaves).

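### LUM-negative tissue is verified mainly through the margin, so passing the 40% and 60% goals shows a positive Youden index only against the plan's hierarchical truth standard

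*SAP*

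**What the plan says.** SAP 3.2.2 gives the reason for the hierarchy: "Because a LUM-guided shave does not exist when a negative LUM image is indicated we propose a hierarchical approach". Protocol 15.2 says the same from the other side: "therapeutic shaves were taken only when the LUM imaging system signaled positive for potential residual tumor". The tiers are shave histology, then first re-excision, then, where neither exists, "the margin assessment of that orientation is used as truth standard". Protocol 3.3.3.2 defines a re-excision as surgery done "because of positive margins found from the initial lumpectomy procedure", so the second tier also depends on the margin.

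There are a few other routes. A clear mastectomy specimen settles all orientations (SAP 3.2.2: "If a mastectomy is performed as a follow-up surgery and no cancer is found in the mastectomy specimen"). For standard-of-care shaves taken after LUM use as a deviation, SAP 4.11.3 says "if there is a Lumicell image for this SOC shave, then the SOC shave will be used as truth standard for that orientation". LUM-positive orientations left unshaved also drop down the tiers: "they will be evaluated for the per-tissue sensitivity and specificity calculation according the hierarchical approach described in section 3.2.2".

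SAP 4.3.2 and Protocol 15.3.2 set goals of 40% for sensitivity and 60% for specificity, and put the margin's sensitivity for cavity cancer, from Phase C, at about 40%. Both then say that clearing the bounds demonstrates a Youden index above zero and so performance that is not random. SAP 3.2.2 reports Youden without testing it.

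**The concern.** The reference standard depends on the test result. A cancer behind a negative margin is found by shave histology if LUM flags it and the surgeon shaves. If LUM does not flag it, no further tissue is normally examined and the orientation counts as a true negative. True positives are then counted nearly in full and false negatives only in part, which raises sensitivity.

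One error works the other way. A positive margin over cancer-free, LUM-negative tissue that is never re-excised counts as a missed cancer. The pure-DCIS rule makes this foreseeable (SAP 3.1: "For pure DCIS lesions: DCIS present less than 2 mm from the ink"), because Protocol 3.1 leaves reoperation for such close margins to clinical judgment.

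At stake is what a passed sensitivity co-primary means. It could not be read as the share of residual cancers found, or alone as proof of better-than-chance detection of cavity cancer. The residual-cancer co-primary uses shave histology and is unaffected.

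**Working it through.** **The plan's own figures.** By exact binomial at one-sided 2.5%, 70 events against 40% need at least 37 detections (size 0.0199), with power 0.909 at 60%. With 1021 negatives against 60%, the rule is at least 644, with power 0.907 at 65%. The stated 90% is reproduced for both.

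**How much rests on the margin.** SAP 4.5 gives 1021/152 = 6.72 negatives per patient, or about 4.5 LUM-negative results at 65% specificity. Suppose a third of patients were re-excised (background figure, Protocol 3.1) at two LUM-negative orientations each (assumed). Re-excision would then cover (1/3 × 2)/4.5 = 15% of those results. At 20% of patients and one orientation (assumed) it covers 4%. So about 85-96% would rest on the margin alone.

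**A device with no discrimination.** It flags a share q of all tissue, so true sensitivity is q and specificity 1 − q. Let s be the share of LUM-positives shaved and p the prevalence, taken as the SAP's 4% truth-standard rate. Per orientation:

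- TP = pq[s + (1−s)r] + (1−p)q(1−s)f
- FN = p(1−q)r + (1−p)(1−q)f
- expected sensitivity = TP/(TP + FN)

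Images per patient are 1021/152 + 70/268 = 6.98, about 7. Phase C's 1.1 shaves give s = 1.1/(7q): 0.52 at q = 0.30 and 0.45 at q = 0.35. The last column is the exact probability of at least 37/70, ignoring clustering.

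| r | Shaving | f | Expected sensitivity, q = 0.30 / 0.35 | Passes sensitivity |
|---|---|---|---|---|
| 0.40 | all | 0 | 52% / 57% | 47% / 81% |
| 0.40 | all | 1% | 40% / 46% | 2% / 14% |
| 0.40 | 1.1 per patient | 0 | 43% / 47% | 7% / 21% |
| 0.40 | 1.1 per patient | 0.5% | 39% / 43% | 1% / 7% |
| 0.40 | 1.1 per patient | 1% | 36% / 40% | 0.2% / 2% |
| 0.60 | all | 0 | 42% / 47% | 4% / 21% |
| 0.60 | 1.1 per patient | 0 | 37% / 41% | 0.4% / 3% |
| 0.80 | all | 0 | 35% / 40% | 0.2% / 2% |

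For the first row, 0.30/(0.30 + 0.70 × 0.40) = 0.517. With a perfect reference (r = 1, f = 0), q = 0.35 passes 0.2% of the time. Solving p so that the truth-standard-positive rate is 4% raises the rows with f above zero by 2-3 points. Specificity barely moves: 70.0% reads as 70.8% and 65.0% as 65.9% in the first row's setting.

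A simulation of all three co-primaries under the first row's settings gave 48% and 79%. It used GEE with ICC 0.22 and 369 device patients (406 × 10/11).

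**When the two errors cancel.** With all positives shaved, inflation disappears when false-positive margins replace the uncounted misses: f = (1−S)(1−r)p/[spec(1−p)]. For true sensitivity S = 60% and r = 0.40, this is 0.4 × 0.6 × 0.04/(0.65 × 0.96) = 1.5%, or 1.4% at 70% specificity. For the no-discrimination device it is 2.5%.

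**Read in reverse (f = 0, all shaved).** True = obs/[obs + (1−obs)/r]. An observed 60% means a true 37.5% at r = 0.40, 47% at 0.60 and 55% at 0.80. A lower limit L stays above 40% only if r ≥ 0.4(1−L)/(0.6L). For an observed 42/70 (L = 47.6%) that is r ≥ 0.73; for Phase C's L = 56%, r ≥ 0.52.

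**The case against.** The plan discloses the hierarchy, explains why it is needed and labels its last tier as inferred. Secondary endpoint (a) in SAP 3.3 is already a common-reference check: its denominator, patients with a positive margin after standard of care, is fixed whatever LUM shows. A chance device flagging 30-35% of orientations would score about 30-35% or less there. This stands, but endpoint (a) gives sensitivity only and covers margin-positive patients only. Of the other planned checks, the SOC-margin accuracy analysis is limited to tissue with a later shave or second surgery (SAP 4.13), and the shave-type subgroups (SAP 4.12) keep the same hierarchy. The pre-SOC-shave images (SAP 3.2.3) have shave pathology for both LUM results, but only a pooled analysis is described.

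The high pass rates need every positive shaved and f = 0. At q = 0.30-0.35 that is 2.1-2.5 shaves per patient, against Phase C's 1.1. This also stands, so those cells are an upper end. If 1.1 meant that every positive was shaved, q would be 1.1/7 = 0.16 and expected sensitivity 32%. That q does not fit 70% specificity, and the documents do not explain the gap.

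A reader might infer that sensitivity is certainly inflated. The documents do not support that. They do not say how the 40% was derived or whether it holds in LUM-negative tissue, and an f near 1.5%, about 25 orientations (369 × 7 × 0.4 × 0.6 × 0.04), would cancel the inflation for a true 60% device. A reader might also infer that the device lacks discrimination. Phase C's 67-69% is above the 52% expected by chance at 70% specificity and r = 0.40.

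**Conclusion.** The concern holds in a limited form. Because LUM-negative tissue is verified mainly through the margin, co-primary sensitivity may be inflated relative to cavity cancer. The size, and at high enough f the net direction, cannot be settled from the documents. At r = 0.40 a no-discrimination device passes the sensitivity test from near 0% to about 80% of the time, and about 7-21% at Phase C's shave rate with f = 0. Passing 40% and 60% therefore shows Youden above zero against the hierarchical standard only; the step to non-random detection of cavity cancer does not follow. These figures rest on assumed r, f and s, on error-free shave histology, on 4% as prevalence, and on margin status being independent of the LUM result given cancer. The planned test and its power arithmetic are sound.

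**What to change.** Keep the primary test unchanged.

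1. In SAP 4.3.2 and Protocol 15.3.2, state that the Youden result is relative to the hierarchical truth standard and delete the clause on non-random performance. Label the sensitivity and specificity co-primaries the same way.
2. Report accuracy for the pre-SOC-shave images separately as well as pooled, stating that this is not the intended-use setting.
3. Pre-specify a supportive analysis of co-primary sensitivity over a grid of r and f. One workable form: among M LUM-negative orientations with x positive through the margin route, estimated cancers are (x − fM)/(r − f); treat unshaved LUM-positives likewise and add the shave-confirmed cancers. Do not add separately any cancers found behind negative margins, because the estimate already covers them. Give the combinations of r and f at which the lower bound stays above 40%, and state the independence assumption.

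An analysis using the margin as truth for every image is optional. It would score cancers found behind negative margins as false positives.

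The cost is wording in two documents and a few tables from data already collected, with no new patients or procedures. The supporting figures may be less favourable.

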3.2.3 Additional sensitivity and specificity analysis

In the pivotal study protocol, images of the cavity are being recorded with the LUM Imaging System before the surgeon removes any SOC shaves. These images are saved with the tumor detection inactive to prevent potentially influencing surgeon's decision to remove the SOC shave. This procedure was implemented to acquire additional data for a potential future use of the LUM Imaging System before removing SOC shaves. However, this procedure does not represent the initial intended use of the LUM Imaging System, more so with the tumor detection algorithm turned off. The initial intended use of the LUM Imaging System is after the SOC procedure including removal of SOC shaves, is completed. Thus, the primary analysis for sensitivity and specificity to support the co-primary endpoints will be done with imaging data collected after the SOC procedure is completed, that is, based on therapeutic shaves, second surgery and prior margin using a hierarchical approach as described in Table 1. As part of the pivotal trial analysis, a secondary evaluation of sensitivity and specificity will include the results from the LUM imaging of the cavity prior to removing SOC shaves.

LUMICELL CONFIDENTIAL

This document is confidential. Do not disclose or use except as authorized.

3.3 Secondary endpoints

- a. Proportion of patients with positive margins after standard of care breast-conserving surgery who have a LUM Imaging System signal in the cavity above the threshold as defined by the tumor detection algorithm (i.e., a positive LUM signal). The endpoint is mathematically defined as:

$$\frac{\# \text{ positive margin patients after SOC with LUM signal above the threshold}}{\# \text{ positive margin patients after SOC}}$$

If a subject has more than one orientation with an SOC positive margin, LUM imaging must correctly identify all orientations with an SOC positive margin for success of this endpoint.

- b. Proportion of subjects with pathology-positive margins after standard of care breast-conserving surgery for whom additional LUM Imaging System-guided shaves resulted in pathology-negative margins. Note: This endpoint also estimates the potential reduction in re-excision surgeries following standard of care breast-conserving surgery that resulted from a positive SOC margin. This is estimated as:

$$\frac{\# \text{ positive margin patients after SOC with all final negative margins after the LUM procedure}}{\# \text{ positive margin patients after SOC}}$$

- c. Proportion of subjects with pathology-positive margins after standard of care breast-conserving surgery for whom additional LUM Imaging System-guided shaves resulted in pathology-negative margins among all patients. This is estimated as:

$$\frac{\# \text{ positive margin patients after SOC with all final negative margins after the LUM procedure}}{\text{Total number patients}}$$

- d. Ratio of patients with negative margins after the SOC procedure who have residual cancer found in at least one Lumicell-guided (or therapeutic) shave among patients with negative margins. This is estimated as:

$$\frac{\# \text{ negative margin patients after SOC with residual cancer found in at least one therapeutic shave}}{\# \text{ negative margin patients after SOC}}$$

- e. Ratio of patients with negative margins after the SOC procedure who have residual cancer found in at least one Lumicell-guided (or therapeutic) shave among all patients

$$\frac{\# \text{ negative margin patients after SOC with residual cancer found in at least one therapeutic shave}}{\text{Total number of patients}}$$

- f. Mean and median incremental volume (in cubic centimeters) of tissue removed from therapeutic shaves: For each patient, absolute shave volume will be calculated as length (c) × width (c) × depth (c) for each therapeutic shave with the sum by patient of all therapeutic shaves. Subjects with no therapeutic shaves taken will have a therapeutic shave volume of 0cc.

- g. Mean and median contribution of therapeutic shave volume to total tissue removed.

LUMICELL CONFIDENTIAL

This document is confidential. Do not disclose or use except as authorized.

- h. Average number of SOC and therapeutic shaves taken per subject overall and by type of SOC lumpectomy procedure (i.e., lumpectomy with comprehensive shaves vs. lumpectomy with or without selective shaves).
- i. Number of second surgeries recommended as a result of final positive margins.
- j. Rate of second surgeries as a result of a positive margin status following SOC (control arm) and LUM Imaging procedures (device arm).
- k. Rate of cancer found in second surgeries
- l. Number of second surgeries for each patient
- m. Number of images per subject from the cavity after SOC and first round of therapeutic shaves
- n. Secondary analysis of sensitivity and specificity including imaging before removal of SOC shaves.
- o. Number of device issues and malfunctions and their impact to data capture.
- p. Patient-level sensitivity and specificity
- q. Collect exploratory data on tissue types found in therapeutic shaves.
- r. Collect exploratory data on patient reported outcomes.
- s. Analysis of tissue-level sensitivity and specificity for the SOC procedure based on the outermost SOC resected surface.
- t. Adverse events stratified by severity and relatedness to drug/device.
- u. Serious adverse events stratified by severity and relatedness to drug/device
- v. Adverse events by preferred term (sorted by descending occurrences for each preferred term).
- w. Summary of adverse events, overall and split by expectedness to drug/device.
- x. Comparison of adverse events in subjects that have at least one therapeutic shave versus subjects that have no therapeutic shaves.

4 Statistical methods

